### **LPs in asymptomatic patients**

In most study OPCs, asymptomatic, CrAg-positive patients will not be offered or referred for LP and CSF analysis since Vietnam National HIV Guidelines do not support the routine use of this invasive procedure in persons who do not have clear clinical features of a CNS infection [15]. Additionally, after discussions with multiple stakeholders at hospitals, conducting LPs on all asymptomatic CrAg-positive patients was felt to be unfeasible due to the limited availability of skilled clinicians and supplies for the procedure. However, patients who are CrAg-positive will be informed by the provider of the possibility of subclinical meningeal disease which can only be diagnosed by LP. If the treating doctors suggest LP to any patients who wish to pursue an LP outside of the program, they will be referred to an appropriate hospital. Study LFA may be used on serum or CSF as part of work up for patients with suspected meningitis.

### **Patients who refuse fluconazole**

Patients who meet the indications for preemptive treatment with fluconazole but decline the treatment will have a one-on-one meeting with a designated clinic staff to ensure they understand the benefits of the antifungal therapy as well as the risks of not taking recommended treatment. If, after this meeting, patients still decline treatment with fluconazole, they will be strongly counseled about the need to return to the clinic for evaluation for symptoms consistent with cryptococcal disease. Patients will continue to be enrolled in the study and the collection of outcomes will continue.

### **Symptomatic patients**

Plasma CrAg-positivity in a person with symptoms consistent with meningitis increases the suspicion for CM. If symptoms of meningitis (e.g., fever, headache, stiff neck) are determined by the treating physician to be present in a CrAg-positive patient, the patient will be referred to the nearest hospital capable of performing an LP and CSF analysis according to national protocols. Data from the hospitalization will be collected for analysis (Appendix 7:

Hospitalization ); however, evaluation and treatment of study participants with symptoms of meningitis will be determined by the treating physician in accordance with national guidelines. Patients with laboratory-confirmed CM will receive induction, consolidation, and maintenance phase therapy as per the Vietnam National HIV Guidelines. These might include intravenous amphotericin B 0.7-1mg/kg/day or high-dose fluconazole for two weeks (induction phase), followed by fluconazole 900 mg/day for 8 weeks (consolidation phase). At the end of the consolidation phase, fluconazole 200mg/day will be prescribed as secondary prophylaxis until  $CD4 >200$  cells/ $\mu l$  for at least 6 months or after viral suppression. This is according to the national protocol and is not considered part of this evaluation [15, 16].

Symptomatic CrAg-positive patients who refuse to have an LP or in whom an LP cannot be done will be offered the same treatment as laboratory-confirmed cases of CM, as outlined in the National Guidelines. If the patient refuses treatment for CM, they will be given oral fluconazole at the same dosage/length as asymptomatic CrAg-positive patients as a final option.

Patients admitted for treatment of CM will remain in the study, and the study point to contact (POC) at the OPC will be responsible for keeping in contact with the hospital to monitor the progress and document the patient's outcome. The OPC staff will abstract information from the inpatient medical record and fill in the study Hospitalization Form (see Appendix)

If, based on laboratory testing, the diagnosis of CM is excluded in patients suspected to have had meningitis (based on presence of fever, headache, or stiff neck) on initial evaluation, they will be treated by using the same protocol as asymptomatic CrAg-positive patients, i.e., started on fluconazole treatment for early cryptococcal disease (900 mg daily for 2 weeks) immediately after CM has been ruled out. This may be started during hospitalization (if patients remain hospitalized for other indications) or upon discharge from the hospital (if no other indication for hospitalization exists). All patients in whom CM is excluded should be provided with fluconazole upon discharge from the hospital so that treatment is not interrupted between hospital discharge and the next OPC appointment. After discharge, patients shall return to the OPC within two weeks to continue pre-emptive treatment as shown in Figure 1 below;

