#### **7.4. Management of a positive CrAg result**

##### **a. Management of a CrAg-positive result - Phase 1**

###### **Asymptomatic patients**

Patients with a positive CrAg test, and who consent to study participation will undergo routine examination at the OPC including assessment for presence of symptoms of meningitis (see Appendix). Patients who are plasma CrAg-positive but do not have symptoms of meningitis will be started on high-dose fluconazole as treatment for early cryptococcal infection.

The optimal antifungal regimen in the population with isolated plasma CrAg remains to be determined.[11] The WHO Rapid Advice recommends that patients with isolated plasma CrAg-positivity should be treated with fluconazole 800 mg/day (or 12 mg/kg/day up to 800 mg/day if aged below 19 years) for two weeks, then 400 mg/day (or 6 mg/kg/day up to 400-800 mg/day if aged below 19 years) for eight weeks, and continued maintenance with fluconazole 200 mg/day is recommended [11]. In this program, maintenance fluconazole will be continued until  $CD4 > 200$  cells/ $\mu L$  for at least 6 months.

In Vietnam, the 150 mg tablet of fluconazole is the standard formulation and widely available for use in the national HIV treatment and care program for the treatment of CM. For this programmatic roll out, fluconazole dosage differs slightly from that recommended by the WHO recommendations but is in line with readily available formulations (150 mg tablets) in Vietnam, and with the updated national guidance [16]. The initial dosage of fluconazole in CrAg-positive patients therefore will be 900 mg taken each day for 2 weeks (WHO recommends 800mg). This will be followed by fluconazole 450 mg orally each day for 8 weeks. Finally, maintenance treatment with fluconazole 200mg orally each day will continue until  $CD4 > 200$  cells/ $\mu L$  for at least 6 months. In accordance with the 2016 WHO guidelines, if HIV viral load monitoring is not available, fluconazole treatment will be continued until patient is stable and adherent to ART and antifungal maintenance therapy for at least one year. If HIV viral load monitoring is available, fluconazole treatment will be continued until patient is stable and adherent to ART and antifungal maintenance treatment for at least one year and has a suppressed viral load. Maintenance treatment after 6 months will be supported by VAAC with dosage of 150 mg per day as same dose as recommended by national

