guideline for treatment of cryptococcal meningitis during maintenance therapy. VAAC is responsible for coordinating ART and OIs drug throughout the country, and they commit to support a full supply of fluconazole for patients enrolled in the screening program. Study findings will inform supply chain and other fluconazole logistical issues. During treatment, development of adverse events (AEs) or side effects related to the use of this drug will be assessed during routine visits to each OPC and managed according to national protocols.

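### Section 7.4 gives two values, 200 and 150 mg/day, for the national fluconazole maintenance dose in cryptococcal meningitis, and the 200 mg pre-emptive maintenance step does not fit the 150 mg tablet on which the programme's doses are said to rest

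*Protocol*

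**What the plan says.** Two parts of Protocol section 7.4 a (Phase 1 management of a positive CrAg result) speak to the national maintenance dose in CM.

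- **Symptomatic patients.** For laboratory-confirmed CM: "At the end of the consolidation phase, fluconazole 200mg/day will be prescribed as secondary prophylaxis". The paragraph closes: "This is according to the national protocol and is not considered part of this evaluation". It cites the 2009 and 2015 Ministry of Health guidance. Patients with symptoms who refuse a lumbar puncture, or in whom none can be done, are offered the same treatment.
- **Asymptomatic patients.** For pre-emptive treatment: "Maintenance treatment after 6 months will be supported by VAAC with dosage of 150 mg per day as same dose as recommended by national", and the sentence goes on: "guideline for treatment of cryptococcal meningitis during maintenance therapy".

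On the tablet, the Asymptomatic patients text says: "In Vietnam, the 150 mg tablet of fluconazole is the standard formulation and widely available for use in the national HIV treatment and care program", with treatment of CM as the stated use. It explains that the programme's dosage departs slightly from the WHO recommendation but "is in line with readily available formulations (150 mg tablets) in Vietnam, and with the updated national guidance". The pre-emptive regimen is then 900 mg/day for 2 weeks, 450 mg/day for 8 weeks and 200 mg/day as maintenance. The 200 mg step is repeated under Follow-up Visits in section 7.7 and in the Phase 1 Overview of section 10.

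**The concern.** The two statements claim to report the same thing, the dose that national guidance recommends for maintenance in CM, and they differ. A reader who uses the protocol to learn that dose gets a different answer depending on the paragraph consulted.

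The tablet question is separate. The protocol gives the 150 mg tablet as the reason for departing from the WHO doses, yet its own maintenance step is not a multiple of 150 mg and nothing explains the exception.

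CM patients remain in the study. They count towards 12-month all-cause and CM-related mortality (Table 1, objective 4), and provider costs of CM treatment are an objective (Table 1, objective 8). Section 8.4 also asks monitors to check that fluconazole dosing of CrAg-positive patients follows section 7.4, which is where the two values stand.

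**Working it through.** No sample size, power or error rate is involved. The check is a comparison of text and a division by tablet strength.

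**1. The two statements side by side**

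| | Symptomatic patients | Asymptomatic patients |
|---|---|---|
| Dose | 200 mg/day | 150 mg/day |
| Prescribed for | Confirmed CM, after consolidation | Pre-emptive patients, after 6 months |
| Said to be | According to the national protocol | The national guideline's dose for CM maintenance |

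The patients for whom the dose is written differ, so the second row alone is no conflict. The conflict is in the third row: each statement equates its figure with the national CM maintenance dose. As written, both cannot be right.

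Size of the difference: 200 − 150 = 50 mg/day. 50/150 = 33%, so 200 is a third above 150. 50/200 = 25%, so 150 is a quarter below 200.

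**2. Doses against the 150 mg tablet**

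Tablets = daily dose / 150.

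| Pre-emptive step | WHO dose as the protocol reports it | Programme dose | Tablets of 150 mg |
|---|---|---|---|
| First 2 weeks | 800 mg (800/150 = 5.33) | 900 mg | 900/150 = 6 |
| Next 8 weeks | 400 mg (400/150 = 2.67) | 450 mg | 450/150 = 3 |
| Maintenance | 200 mg (200/150 = 1.33) | 200 mg | 200/150 = 1.33 |
| Maintenance after 6 months | none given | 150 mg | 150/150 = 1 |

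The first two WHO steps were moved to whole tablets. The third was left as it was and is the only programme dose that is not a whole number of the stated tablet. The protocol names no other strength.

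**3. Who is affected**

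Section 6 projects about 29 CrAg-positive patients by the end of Phase 1. The CM contradiction concerns an unknown part of them, and section 10.2 notes that few had developed CM so far. The tablet mismatch concerns those on the pre-emptive regimen who reach maintenance.

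**The case against.** The strongest answer is that the protocol does not control CM treatment. Only the Symptomatic patients text says what a CM patient receives. The 150 mg figure is an instruction for pre-emptive patients after 6 months, and CM enters only as a comparison. The Symptomatic patients text leaves evaluation and treatment to the treating physician under national guidance and places the regimen outside the evaluation, so the clinician's working source is the guideline itself. This stands as a limit on consequences. It does not remove the contradiction, because both statements claim to report that guideline.

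A second answer concerns the tablet. The statement about 150 mg tablets explains the pre-emptive doses, and the protocol does not claim that CM doses were derived from that tablet. Standard and widely available also does not mean the only strength, and section 10.1.1 lists the formulation of fluconazole as a recorded variable. This too stands in part: the mismatch should be charged to the pre-emptive maintenance step, and it is an unexplained exception rather than proof that the dose cannot be dispensed.

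Third, the effect on results is not shown. The two outcomes used for precision in section 6, the proportion with a low CD4 count and the CrAg prevalence, do not depend on maintenance dose. Costs are collected retrospectively from facility data systems or staff interviews (section 10.2), so CM costing need not rest on the dose printed in section 7.4. This is accepted.

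A reader might go further and infer that sites do give CM patients different doses, or that they round 200 mg to one or two tablets. No passage says either. A reader might also assume that the study already records the maintenance dose given to CM patients. The fluconazole log (Appendix 19) and the current-dose item in section 10.1.2 are described for pre-emptive therapy, so the documents do not show this.

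**Conclusion.** The point holds as a fault of documentation, in two parts.

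- Section 7.4 gives two values, 200 and 150 mg/day, for the national CM maintenance dose. This rests only on the protocol's own attribution of each figure to national guidance. Which figure is right cannot be judged from the documents.
- The 200 mg pre-emptive maintenance step (sections 7.4, 7.7 and 10) is 1.33 of the 150 mg tablets with which the programme's doses are said to be in line, and no other strength is named.

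Different dosing between sites is a possible consequence, not something established. The likely effect on study results is small, because few patients are concerned and the protocol hands CM treatment to clinicians under national guidance. It still deserves correction: a written treatment dose contradicts itself in the very section that monitors are told to check dosing against, and the repair is cheap.

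**What to change.** 1. Check the Symptomatic and Asymptomatic patients texts of section 7.4 a against the cited national guidance, and state one national maintenance dose for CM, in the same terms in both places.
2. Make the pre-emptive maintenance dose and the stated tablet formulation agree in section 7.4 a, under Follow-up Visits in section 7.7, and in the Overview of section 10. If another strength is meant to be used, name it there.
3. The clinical team decides the values. This review proposes none.

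The cost is wording in a protocol amendment and a short memo to sites. It needs no additional patients, visits or procedures.

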## **b. Management of a CrAg-positive result- Phase 2**

[figure not shown]
## Cryptococcal Retention In Care Study (CRICS)

Under Phase 2, upon the receipt of CrAg positive test results from CRICS labs, the patient's primary providers will be responsible for prescription of fluconazole and follow up according to their standard care procedures and national guidelines. Fluconazole will be donated to selected facilities for CrAg-positive patients if not otherwise readily available free of charge at the participating site.

Patients will not be enrolled in longitudinal follow up. No clinical data will be collected apart from CD4 count, indication for CD4 test, and CrAg result, and in CrAg-positive patients, whether fluconazole treatment was initiated. In addition, we will document number tested, number who are CrAg positive, and the respective CD4 counts.

Cryptococcal Retention In Care Study (CRICS)

**Figure 1: Management of Patients Enrolled in the CrAg Screening Program in Phase 1**

## 7.5. Fluconazole therapy

### Toxicity

Fluconazole is a safe, widely used antifungal medication. The main side effects are nausea, headache, skin rash, abdominal pain, vomiting and diarrhea[18]. In a study of high-dose fluconazole for HIV-associated CM in Uganda, fluconazole at both dosages of 800 mg/day and 1200 mg/day appeared to be well tolerated. No patients discontinued fluconazole therapy because of suspected AEs before completing 14 days of treatment. Although fluconazole can cause liver dysfunction, in this study there was no statistically significant difference between the 2 dosage groups in the percentage change in alanine aminotransferase (ALT) and serum glutamic pyruvic transaminase (SGPT) level [19].

### Special populations

*Pregnancy:* Fluconazole, a US Federal Drug Administration Category D medication, has been shown to be teratogenic in the first trimester of pregnancy. For this reason, it is contraindicated during the first trimester. Further, the effects of prolonged high-dose fluconazole later in pregnancy have not been confirmed.

According to the Vietnam Guidelines for Diagnosis and Treatment [15] all ART-eligible female patients should have an initial assessment with obstetric, gynecological history and use of contraceptive methods documented. A urine pregnancy test is done based on need. For this study, a urine pregnancy test will be performed for all CrAg+ women of reproductive age (18–49 years old) at the enrollment visit and during follow up in those where pregnancy is suspected (last normal menstrual period (LNMP) is > 5 weeks). Pregnancy is an exclusion criterion for study enrollment of CrAg+ women.

Women who enroll in the study (Phase 1) will be given informed consent regarding the effects of fluconazole in pregnancy and its contraindication in pregnancy. During the consent process, they will be told that pregnancy testing will be required at enrollment and at any follow-up visits if they have missed a period. They will be strongly encouraged to use a modern contraceptive method during the course of the study, and will be told to stop fluconazole immediately and to come to the clinic if they suspect pregnancy.

At each study visit, for CrAg+ women of reproductive age, study staff will highlight the importance of not getting pregnant, the effect of fluconazole for pregnancy, and discuss contraceptive methods. Each of these women will be asked about her LNMP and her

## Cryptococcal Retention In Care Study (CRICS)

contraceptive use. These data will be noted in the study records. If a female participant's LNMP is > 5 weeks before the current visit, a urine pregnancy test will be performed to rule out pregnancy.

Fluconazole will be discontinued immediately for women who become pregnant during the study period because of the drug's teratogenicity during the first trimester. Pregnancy in these study participants will be considered a serious adverse event (SAE), reportable to the institutional review boards (IRBs) and funder.

*Other relevant contraindications:* Patients with other relative contraindications will be advised accordingly. Patients with known liver disease, patients starting ART on anevirapine (NVP)-containing regimen, and patients on certain anti-tuberculosis (TB) medications will be given the following information and advised accordingly.

- **Patients with a history of liver disease:** Patients with cirrhosis, hepatitis, jaundice, or abnormal liver enzyme tests (>2x upper limit of normal) will receive careful monitoring for signs of liver damage after beginning fluconazole treatment. These signs include right upper quadrant pain, nausea/vomiting, and jaundice. If signs of liver damage are present, liver function tests will be ordered and evaluated.
- **Patients starting ART:** Patients on fluconazole starting ART will not be started on an NVP-containing regimen to avoid the synergistic hepatotoxicity of NVP and fluconazole treatment. For these patients, efavirenz (EFV) will be considered if there are no contraindications.
- **Patients with renal failure:** Fluconazole is primarily renally excreted, thus dosing in patients with impaired kidney function needs to be adjusted based on the patient's creatinine clearance. Discussion with a senior physician is recommended for patients who have impaired creatinine clearance to appropriately dose their fluconazole.
- **Patients with TB/HIV Co-infection:** Because both fluconazole and TB medications can cause hepatotoxicity, patients co-infected with TB will be started on an ETV-based rather than an NVP-based ART regimen. Patients will be monitored closely for signs and symptoms of hepatotoxicity such as right upper quadrant abdominal pain, nausea/vomiting, or jaundice. If there are signs of toxicity, then liver function tests will be ordered and evaluated and managed as outlined in the sections below.

### **Management of hepatotoxicity**

## Cryptococcal Retention In Care Study (CRICS)

Patients with hepatotoxicity will be managed according to the national guidelines[15].

- Management of hepatotoxicity when patients are on ART:
  - If ALT increases to grade 3 and the clinical status of the patients is stable, ART will be continued with less hepatotoxic drugs, such as EFV; with monitoring of ALT levels closely (every 2 weeks) and of the clinical symptoms;
  - HIV/HBV co-infected patients on 3TC, TDF will be monitored closely if they have to stop antiretroviral (ARV) drugs, for any reason.
- Management of NVP Hepatotoxicity:

Grade	ALT	Management
Grade 1(Mild)	1.25 - 2.50 times upper normal limit	Continue with NVP. Monitor ALT closely in every 2 weeks
Grade 2 (Moderate)	2.60 – 5 times upper normal limit	
Grade 3 (Severe)	5 - 10 times upper normal limit	STOP NVP immediately. Continue with other 2 drugs for 7 days, then replace NVP by EFV if ALT improves or If ALT is not improved, stop other 2 drugs. Restart ART only when ALT has improved; replace NVP with EFV-based regimen.
Grade 4 (Severe life-threatening)	> 10 times upper normal limit	Take into account both ALT and clinical signs and symptoms for appropriate management. The ARV regimen can be stopped, patient hospitalized, or referred to higher level. Restart ART with NVP substituted with EFV or TDF or LPV/r on case-by-case basis

### 7.6. ART

Since 2011, the recommended first-line prioritized ART regimen in Vietnam includes tenofovir, lamivudine, and dideoxy-nucleoside reverse transcriptase inhibitor (NNRTI), either EFV

## Cryptococcal Retention In Care Study (CRICS)

or NVP. This regimen is used for all ART initiators by national guideline unless there are contraindications to any of the drugs[20].

The optimal timing of ART initiation among patients with isolated CrAg-positivity (no evidence of CM) has not yet been established. In this program, initiation of ART will be delayed by 2 weeks in those who are CrAg-positive to enable completion of 2 weeks of pre-emptive therapy with fluconazole. This delay is intended to prevent development of IRIS. The ART regimen selected will follow national guideline with a preference for EFV over NVP. CrAg-negative patients will be evaluated at those clinics according to routine protocols and evaluated and initiated on ART, as appropriate.

For patients with CM, the optimal timing of ART initiation has also not been established. However, the Cryptococcal Optimal ART Timing Study (ClinicalTrials.gov identifier NCT01075152), conducted in Uganda, aimed to evaluate early ART initiation after CM diagnoses (7-11 days after receipt of amphotericin B) versus late ART initiation (5 weeks after receipt of amphotericin B). This trial was stopped early after interim results from the study's Data Safety Monitoring Board review showed increased mortality among patients who were in the early ART initiation group[21]. Thus, in this program ART initiation will be deferred for at least 2-5 weeks after the start of antifungal treatment in order to comply with the best evidence to-date and national guidance [16].

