### **Follow-up Visits**

- CrAg-positive patients without symptoms of cryptococcal disease will be seen back at clinic **after two weeks** for evaluation and changing of their fluconazole dose to 450 mg per day (to be taken for 8 weeks) and initiation on ART as per the evaluation guidelines (see Appendix 5: Starting ART Form). They will subsequently return to clinic for an

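### Section 7.6 leaves nevirapine as second choice for CrAg-positive patients, who on schedule start ART while on fluconazole; Section 7.5 bars that combination

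*Protocol*

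**What the plan says.** Section 7.6 opens with the national first-line regimen, in which the third drug is either EFV or NVP unless a drug is contraindicated. Its next paragraph concerns isolated CrAg-positivity. There it says that "initiation of ART will be delayed by 2 weeks in those who are CrAg-positive", and continues: "The ART regimen selected will follow national guideline with a preference for EFV over NVP". The sentence after that turns to CrAg-negative patients. Section 7.6 does not refer to 7.5.

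Section 7.5, in its bullet on patients starting ART, states: "Patients on fluconazole starting ART will not be started on an NVP-containing regimen to avoid the synergistic hepatotoxicity of NVP and fluconazole treatment". It adds that EFV is to be considered where not contraindicated, and it names no other option in that bullet.

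Section 7.4 sets the fluconazole course for asymptomatic CrAg-positive patients. After two weeks at 900 mg/day, "This will be followed by fluconazole 450 mg orally each day for 8 weeks", and then "maintenance treatment with fluconazole 200mg orally each day will continue until" a CD4 criterion is met. Section 7.7 sets the two-week visit for "changing of their fluconazole dose to 450 mg per day (to be taken for 8 weeks) and initiation on ART".

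Section 7.4 also covers CrAg-positive patients who decline fluconazole: "Patients will continue to be enrolled in the study and the collection of outcomes will continue".

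**The concern.** Two operative instructions cover the same treatment decision and differ in strength. One is a bar with its reason given, and the other is a ranking. The weaker one stands in the section that a clinician would open to choose an ART regimen. At stake is a drug interaction that the protocol itself identifies as hepatotoxic.

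The difference matters most for a patient who cannot take EFV. Section 7.5 then says no to NVP without saying what to give. Section 7.6, with two listed options and EFV ruled out, points to NVP.

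**Working it through.** **1. Are the patients under 7.6 on fluconazole when ART starts?** Inputs: 900 mg/day for 2 weeks and 450 mg/day for 8 weeks (Section 7.4); ART start at 2 weeks (Sections 7.6 and 7.7).

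- Planned pre-emptive course: 2 + 8 = 10 weeks.
- Part that falls after ART start: 10 - 2 = 8 weeks, or 8 x 7 = 56 days. That is 8/10 = 80% of the course.
- Maintenance at 200 mg/day follows.

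Section 10 places the step down to 450 mg and ART initiation together as well. An asymptomatic CrAg-positive patient who accepts fluconazole and keeps the schedule is therefore under the 7.5 bar when the 7.6 rule is applied.

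**2. The two rules side by side.**

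| Situation at ART start | Section 7.5 | Section 7.6 |
|---|---|---|
| On fluconazole, EFV tolerable | No NVP; consider EFV | EFV preferred |
| On fluconazole, EFV contraindicated | No NVP; no alternative named | NVP remains as second choice |
| CrAg-positive, not on fluconazole | Bar does not apply | EFV preferred |

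The first row agrees in practice, the second conflicts, and the third is coherent.

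**3. How many patients could a wording change reach?** Inputs from Section 6: 957 enrolled and 25 CrAg-positive by 31 October 2016, about 13 months, 74 enrolments per month, and 1,104 enrolled with about 29 CrAg-positive expected at the end of Phase 1.

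The plan's own figures reproduce:
- 957/13 = 73.6 per month, given as 74.
- 1,104 x 25/957 = 28.8, given as about 29.

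The remaining enrolment depends on the closing date:
- Section 6 total: 1,104 - 957 = 147 further enrolments, and 147/74 = 2.0 months. This takes enrolment to the end of December 2016, the date on the Phase 1 row of Table 3. Expected CrAg-positive: 147 x 25/957 = 3.8.
- Section 3 dates: enrolment runs to March 2017. From November that is 5 months. Expected CrAg-positive: 5 x 74 x 25/957 = 9.7.
- Section 3 equates March 2017 with projected approval of the amendment. If enrolment stops at approval and the change takes effect only then, it reaches almost no new enrolments. Section 10, however, plans data items for patients enrolled after approval, so some later enrolment was foreseen.

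The range is about 0 to 10 new CrAg-positive enrolments, less any who decline fluconazole, plus those among the 25 who have not yet started ART. The last number is not given.

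**The case against.** The strongest reply is that the sections are compatible. Section 7.5 comes directly before 7.6 and gives the specific rule, 7.6 gives the general direction, and choosing EFV satisfies both. That stands for any clinician who reads both sections and can give EFV. It does not settle the case where EFV is contraindicated.

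A second reply is that 7.6 excepts contraindicated drugs, and that 7.5 lists NVP with fluconazole under contraindications, so NVP is already excluded. This does not hold. The list in 7.5 concerns relative contraindications to fluconazole. Its lead-in speaks of patients starting an NVP-containing regimen as people to be informed and advised, which presupposes that some will do so. Nor does 7.6 make the link: if NVP were excluded for these patients, there would be nothing to rank EFV above.

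A third reply is that a softer rule has its place, because some CrAg-positive patients are off fluconazole: those who decline it, become pregnant or stop after a serious adverse event. This is fair, and the preference can stay for them. But 7.6 does not limit it to them.

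A reader might infer that the protocol endorses giving NVP with fluconazole, or that patients have received the combination. The documents support neither: the bar is explicit in 7.5, and nothing is reported on regimens given. A reader might also take 29 - 25 = 4 as the most patients that a change could reach. That figure reflects only about two months of further enrolment, so it is not an upper limit.

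**Conclusion.** The inconsistency is real and minor. For treated CrAg-positive patients, 7.6 is weaker than 7.5 on a safety instruction. The two give different answers when EFV is contraindicated or when 7.6 is consulted alone.

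The conclusion assumes that the preference sentence applies to CrAg-positive patients, as its position in the paragraph indicates, and that they take fluconazole on schedule. The reach of roughly 0 to 10 new enrolments further assumes the observed 25/957 positivity and 74 enrolments per month. How many would be given NVP cannot be estimated from the protocol, and the 56-day overlap describes exposure, not risk. No endpoint, estimate or sample size depends on the point.

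**What to change.** In 7.6, replace the preference sentence with a rule of this kind: do not start nevirapine in any CrAg-positive patient taking fluconazole (see 7.5); give efavirenz or, where efavirenz is contraindicated, a regimen without nevirapine. Keep the preference for EFV for CrAg-positive patients who are not on fluconazole. The investigators should name the alternative. Section 7.5 already mentions LPV/r as a case-by-case substitute in its table on NVP hepatotoxicity.

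A clerical correction can go in at the same time. The TB bullet of 7.5 reads "patients co-infected with TB will be started on an ETV-based rather than an NVP-based ART regimen", where ETV should be EFV.

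The cost is one sentence in 7.6 and one corrected abbreviation in 7.5, with no added visits, tests or data.
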